## 1.0 PROTOCOL SYNOPSIS

Study Title:	A Prospective, Multi-Center, Non-Randomized Study to Evaluate the Quality of Life Impact After Treatment for Nasal Airway Obstruction Using the Aerin Vivaer™ Stylus
Investigational Device:	Aerin Medical Vivaer™ Stylus
Subject Population:	Male and female subjects who previously completed participation in the Aerin Medical Nasal Obstruction study
Study Procedure:	Subjects who have completed the Aerin Medical TP 258 study, "A Prospective, Multi-Center, Non-Randomized Study to Evaluate Treatment of Nasal Airway Obstruction Using the Aerin Medical Device." will complete the Nasal Obstruction Symptom Evaluation (NOSE) and a brief Aerin Medical Quality of Life Questionnaire
Number of Sites:	Up to 8 study sites
Timepoints:	From procedure: 12, 18 and 24 months

## 2.0 INTRODUCTION AND LITERATURE REVIEW

### 2.1 Introduction

The Aerin Medical Vivaer™ Stylus is a disposable handheld device capable of delivering bipolar radiofrequency energy to tissue and has been used to treat nasal airway obstruction.

Chronic nasal obstruction can elicit many symptoms, including congestion, stuffiness, headache, fatigue, sleep disturbance, daytime sleepiness, snoring and a decline in health-related quality of life (QOL) (Rhee, Book et al. 2003). In recent years, there has been growing awareness that nasal obstruction may impair various daily and social activities (Udaka, Suzuki et al. 2006) and result in a degradation of the patient's overall quality of life (Rhee, Weaver et al. 2010).

### 2.2 Subjective Assessment

Given the significant QOL impact of nasal obstruction, it is important to measure not only the physical symptoms (congestion, obstruction and ability to breathe) but also the impact of those symptoms on the patient's ability to sleep and the related consequences on rest, productivity, concentration and ability to participate in the normal daily activities of work and life.

In addition to the physical benefits of increased nasal patency, there are significant quality of life benefits that are associated with better breathing. After correcting nasal obstruction patients report significantly better sleep function (e.g. better night's sleep; lessened waking up during the night and difficulty falling asleep) as well as better psychological function (e.g. concentration, productivity and frustration). (Brown, Hopkins, et. al). We believe that these benefits may well be durable beyond the initial six months of the study in terms of sustained quality of life impact.

### 2.3 Study Design and Objectives

This is a prospective, non-randomized, multicenter follow-up study to collect long term data on a cohort of patients who participated in the Aerin Medical TP 258 study, “A Prospective, Multi-Center, Non-Randomized Study to Evaluate Treatment of Nasal Airway Obstruction Using the Aerin Medical Device.” The study will be conducted in a maximum of 8 centers. Follow-up data will be collected at the 12, 18 and 24-month post-procedure timepoints for all patients who have completed the above-mentioned study. The objective of the study is to evaluate the long-term durability of benefits associated with the Vivaer Stylus procedure.

### 2.4 Subject Population

The subjects in this study will all have completed participation in the TP 258 Nasal Obstruction study at each center. All subjects will be willing to and agree to participate. Of the original 50 patients in the pivotal trial, 49 would be eligible to participate.

### 2.5 Informed Consent Process

Patients who have gone through the Vivaer procedure and agree to participate in this follow-on study will be asked to sign an informed consent document.

#### Informed Consent

Informed consent will be obtained as outlined in 21 CFR Part 50 and the Good Clinical Practice: Consolidated Guidance (ICH, April 1996).

Prior to participation in the study, the patient or patient’s legal representative must sign an informed consent document.

### 2.6 Data Collection

Follow up data will be collected via telephone, by mail or during office visits. Data will be captured on a Follow-up Case Report Form (CRF).

### 2.7 Types of Assessments

After patients have had the opportunity to ask questions and receive answers, and the study informed consent form is signed, the following evaluations will be completed:

- The Study Staff will administer or ask that patients complete the Nasal Obstruction Symptom Evaluation (NOSE) scale and a brief Aerin Medical Quality of Life questionnaire. These tools can be administered either in the office, by mail or via a phone call.
- These tools will be administered at 12, 18 and 24 months ( $\pm$  6 weeks) after study treatment with the Vivaer Stylus

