**Compared to before you had the procedure, how often do you suffer from the following conditions?**

		Very Rarely/ Never	Rarely	Occasionally	Frequently	Very Frequently
1.	Headaches					
2.	Sinus infections					
3.	Sore throat					
4.	Post nasal drip					

**Compared to the time prior to when you had the procedure, how often have you used each of the following products to help you with nasal congestion/difficulty breathing through your nose?**

		Much less frequently	Less frequently	About the same	More Frequently	Much More Frequently
1.	Oral medications (antihistamines, oral decongestants)					
2.	Nasal sprays (nasal steroids, inhaled decongestants)					
3.	Nasal breathing strips (for example, BreatheRight® Strips)					

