**Figure 1. Aerin Medical Quality of Life survey.**

## 5 STATISTICAL ANALYSIS

Statistical methods are described within the outcome specific subsections that follow. Each subject served as their own control for comparison of preprocedure to postprocedure condition.

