### 5.7 Primary Analysis

Mean NOSE scores at baseline and each follow-up evaluation will be calculated to show the time course progression of improvement. Repeated measures analysis of variance (ANOVA) will be used to test for differences from baseline to follow-up evaluations. The statistical significance level will be set at 5% (p-value < 0.05).

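### A later nasal operation or repeat procedure is neither among the listed follow-up evaluations nor covered by the SAP, so any relief it gave would count as durable Vivaer benefit

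*Protocol*

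**What the plan says.** Protocol 2.3 sets the aim: to "evaluate the long-term durability of benefits associated with the Vivaer Stylus procedure". For follow-up, Protocol 2.7 has patients "complete the Nasal Obstruction Symptom Evaluation (NOSE) scale and a brief Aerin Medical Quality of Life questionnaire", and "These tools will be administered at 12, 18 and 24 months" with a window of 6 weeks either side. Contact may be in the office, by phone or by mail.

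The survey is reproduced in full in the SAP (Figure 1). Its only items on other treatment are three that ask "how often have you used each of the following products to help you with nasal congestion/difficulty breathing through your nose"; they cover oral medications, nasal sprays and breathing strips. SAP 5.8 tabulates the survey answers item by item and does not connect them to NOSE.

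On analysis:
- SAP 5.1 takes in every eligible subject who consented and returned one survey or more.
- SAP 5.7 states: "Repeated measures analysis of variance (ANOVA) will be used to test for differences from baseline to follow-up evaluations".
- SAP 5.8 defines a responder by NOSE change alone, a fall of 15 points or more from baseline, and treats all secondary analyses as exploratory.
- SAP 3.1 confirms that there was no concurrent control and no blinding. The comparison is within subject: "Each subject served as their own control for comparison of preprocedure to postprocedure condition".

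**The concern.** The study asks whether the benefit of one procedure lasts to 24 months. A NOSE score taken after a second procedure, of the same or another kind, no longer measures that. Subjects whose relief fades have the most reason to seek further treatment. If that treatment helps, a subject whose benefit failed appears in the data as one whose benefit lasted. With no control arm, no comparison within the study would show this.

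At stake is how large and how durable the 12- to 24-month benefit appears, both as mean NOSE and as the responder rate.

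**Working it through.** **Step 1. The plan's own figure.** There is no power calculation to reproduce. The maximum of 49 in SAP 3.2 is the number who completed TP258, and it agrees with the 49 of 50 eligible in Protocol 2.4.

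**Step 2. Could a later procedure be caught anywhere?**

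| Place | What it covers | Later procedure? |
|---|---|---|
| Protocol 2.4, SAP 3.2 (eligibility) | Completed TP258, agrees to take part | Not mentioned; a subject re-treated between week 26 and month 12 still qualifies |
| Protocol 2.7 (evaluations) | NOSE and survey | Not listed |
| SAP Figure 1 (survey) | 21 items; 3 on products used | No item |
| Protocol 4.0 (withdrawal) | Four reasons | Not named |
| Protocol 14.0 (site records) | Progress notes, adverse event records | Might hold it; no step moves it into the analysis |
| SAP 5.1, 5.7, 5.8 | Population, ANOVA, responders | No exclusion, flag or failure rule |
| SAP 5.3 | Missed items and surveys | Silent on scores observed after another procedure |

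Repeated measures ANOVA may drop subjects with a missed visit, so not every observed score need enter the primary analysis. But no score is set aside because it follows another procedure.

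**Step 3. Responder rate.** Let k be the number of subjects who were re-treated, would otherwise be non-responders, and reach a 15-point improvement afterwards. The overstatement is 100 × k/n percentage points. Neither k nor the number observed at month 24 is in the documents. I assume k = 1 to 4, and n = 49 (the maximum) or 40.

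**Step 4. Mean NOSE.** If re-treatment lowers NOSE by D points, the mean shifts by k × D/n. D = 30 to 45 is assumed.

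| k | Rate, n = 49 | Rate, n = 40 | Mean shift, n = 49 | Mean shift, n = 40 |
|---|---|---|---|---|
| 1 | 2.0 | 2.5 | 0.6 to 0.9 | 0.75 to 1.1 |
| 2 | 4.1 | 5.0 | 1.2 to 1.8 | 1.5 to 2.25 |
| 4 | 8.2 | 10.0 | 2.4 to 3.7 | 3.0 to 4.5 |

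For example, 4/40 = 10.0%, and 4 × 45/40 = 4.5 points.

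**Step 5. Is even one such event plausible?** With an assumed cumulative re-treatment rate p over 24 months, the chance of at least one among 49 is 1 − (1 − p)^49. This gives 63% at p = 2%, 92% at 5% and 99% at 10%, with 1.0, 2.5 and 4.9 subjects expected. It counts all re-treated subjects, not only those who meet the conditions in Step 3.

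**Step 6. The test against baseline.** For one paired comparison (two-sided 5%, 80% power; sidedness is not stated in the SAP), the detectable standardised change at n = 49 is (1.96 + 0.84)/√49 = 0.40. A test this sensitive is unlikely to turn on a few re-treated subjects. The reported size of the benefit is more exposed than the p-value.

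**The case against.** The strongest reply is that nothing shows the problem arose, and that several stronger readings go beyond the text.

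- A reader might infer that the form holds nothing but the two questionnaires. The Follow-up CRF is not reproduced, and Protocol 2.7 lists evaluations, not form fields. An unlisted field is possible. This stands, although the SAP would still have no rule for using it.
- A reader might infer that the missing information can never be recovered. Protocol 14.0 has sites keep progress notes, medical history and adverse event records, so some could be retrieved. This stands too, although retrieval is not planned and treatment elsewhere could be missed.
- A reader might infer that the bias can only run upwards. A later procedure may fail or make symptoms worse, and re-treated subjects may withdraw. Overstatement is the likely direction, not a certain one.
- The per-subject figures are ceilings. Someone who has partly relapsed but is still 15 points better than baseline adds nothing to the responder rate, which is in any case exploratory.
- The SAP describes collection in the past tense, so a new form item may come too late.

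These points limit the claim. They do not supply a planned way to identify a later procedure or to handle the scores that follow it.

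**Conclusion.** The gap is real, and its effect is conditional. As written, the plan neither lists a later nasal procedure among what is collected nor says how to treat NOSE scores obtained after one. If one occurred and helped, its effect would be reported as durable Vivaer benefit.

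The size is unknown because the number re-treated is not given. On the assumed ranges, two to four qualifying subjects of 40 would overstate the responder rate by 5 to 10 percentage points and shift mean NOSE by 1.5 to 4.5 points on a 100-point scale.

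A reader might conclude that the primary result is wrong. The documents do not support that: they report no re-treatment, and the comparison with baseline is probably robust to a handful of such subjects. The matter should be put right because the correction is cheap and goes to the study's stated objective.

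**What to change.** 1. Record the type and date of any procedure for nasal obstruction since the TP258 treatment. If follow-up is still running, add one item to the Follow-up CRF at each contact, with the first contact reaching back to the treatment date. If it is complete, make a one-time query of subjects and of the site records named in Protocol 14.0. Limit the item to procedures for nasal obstruction, so that unrelated sinus procedures do not count as failures.
2. In SAP 5.7, report mean NOSE with and without scores obtained after such a procedure, with the number of subjects affected. Leaving those scores out removes subjects whose benefit may have failed, so that mean can still be optimistic and should be read beside item 3.
3. In SAP 5.8, beside the planned responder rate, add one that counts a subject as a non-responder at every visit after a procedure for nasal obstruction.

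A responder rule based on the product-use items is not needed. More frequent use can have other causes, such as allergy or a cold, and it says nothing about procedures. At most it could be an optional exploratory table.

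The cost is one question or record query, a few SAP sentences, and a sensitivity responder rate that may be slightly lower. These are analysis rules and restrict no care. If nobody was re-treated, saying so strengthens the durability claim.

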## 3.0 SUBJECT REIMBURSEMENT

Subjects may be reimbursed for their time spent completing the follow-up questionnaires and any expenses associated with each data collection time point, as allowed by study site policies. Subjects will not be reimbursed for incomplete questionnaires.

#### 4.0 STUDY WITHDRAWAL

Subjects may be terminated or withdrawn from the study for the following reasons:

- Voluntary withdrawal – meaning that the subject voluntarily chooses not to further participate in the study
- Lost to follow-up – meaning that the subject is more than one month late (beyond the late data collection window) and 3 documented attempts to contact the subject are unsuccessful. A subject who misses a follow-up time point but completes the questionnaires for a subsequent time point will no longer be considered lost to follow-up.
- In the physician's opinion, it is not in the best interest of the subject to continue study participation.
- Subject death.

Any study subject who does not complete the questionnaires for a specific data collection follow-up should be contacted by site personnel to determine the reason for the missed follow-up. The reason for the missed follow-up should be determined and documented in the subject's study records. All subjects enrolled (including those withdrawn or lost to follow-up) shall be accounted for with appropriate documentation.

#### 5.0 STUDY MANAGEMENT

This study will be conducted in accordance with elements of E6 Good Clinical Practice Consolidated Guidance, ICH, April 1996, Abbreviated Requirements of 21 CFR 812 for NSR device studies, the Declaration of Helsinki, the Belmont Report and any conditions imposed by the reviewing IRB or US FDA or other regulatory agency.

The study sponsor has the overall responsibility for the conduct of the study according to all applicable regulatory requirements. The study sponsor will have certain direct responsibilities and will delegate other responsibilities to the Principal Investigator. The study sponsor and Principal Investigator will ensure that the study is conducted according to all applicable regulations. All personnel to participate in the conduct of this clinical trial will be qualified by education and / or experience to perform their tasks.

The study sponsor, Investigator or any person acting for or on behalf of a sponsor or Investigator shall act in accordance the applicable standards, guidelines and regulations.

#### 6.0 REQUIRED DOCUMENTS FROM THE INVESTIGATOR (PRIOR TO STUDY START)

At a minimum, the following documents will be provided by the investigational site to the study sponsor:

- Signed Investigator Agreement
- Signed Clinical Investigational Plan (CIP) Signature Page
- IRB/EC approval
- IRB/EC approved Informed Consent Form (ICF)

- Investigator and Co-Investigator's current Curriculum Vitae
- Investigator and Co-Investigator's current Medical Licenses

A site may not begin study participation until all the above listed documents have been provided to the study sponsor.

Each study center will undergo protocol initiation including but not limited to a review of the following:

- Procedures for obtaining Informed Consent
- Procedures for completing Informed Consent Form
- Reporting requirements
- CRF completion and correction procedures
- Protection of patient confidentiality

## 7.0 ETHICAL CONSIDERATIONS

The rights, safety and wellbeing of clinical investigation subjects shall be protected consistent with the ethical principles outlined in the Declaration of Helsinki. This shall be understood, observed and applied at every step in this clinical investigation.

It is expected that all parties will share in the responsibility for ethical conduct in accordance with their respective roles in the investigation. The Sponsor and the Investigator shall avoid improper influence or inducement of the patient, study monitor, clinical investigator or other parties participating in or contributing to the clinical investigation.

## 8.0 PROTECTION OF PATIENT CONFIDENTIALITY

At all times throughout the clinical investigation, confidentiality will be observed by all parties involved. All data shall be secured against unauthorized access. Privacy and confidentiality of information about each patient shall be preserved in the reports and in any publication. Each patient participating in this study will be assigned a unique identifier. All CRFs will be tracked, evaluated, and stored using only this unique identifier.

The investigational site will maintain a confidential study patient list (paper or electronic) identifying all enrolled patients. This list will contain the assigned study patient's unique identifier and name. The Site Principal Investigator (PI) bears responsibility for keeping this list confidential. This list will not be provided to the study sponsor and is only to be used at the study center.

Monitors and auditors will have access to the study patient list and other personally identifying information of study patients to ensure that data reported in the CRF corresponds to the person who signed the ICF and the information contained in the original source documents. Such personal identifying information may include, but is not limited to the patient's name, address, date of birth, gender, race and medical record number.

*NOTE: The patient's name, medical record number or address will NOT be recorded in the monitor's visit report or the database; demographic data that may be recorded includes age, race, and gender.*

Any source documents copied for monitoring purposes by the Sponsor will have patient identifiable information redacted and be identified by using the assigned patient's unique identifier in an effort to protect patient confidentiality.

## 9.0 DATA COLLECTION

Study data will be collected using standardized Case Report Forms (CRFs). The CRFs are designed to accommodate the specific features of the trial design. Modification of CRFs will only be made if deemed necessary by the study sponsor.

There is no source data for a questionnaire; the questionnaire itself is the source document.

## 10.0 STUDY SUSPENSION OR EARLY TERMINATION

The study can be discontinued at the discretion of the Site PI or Sponsor for reasons including, but not limited to, the following:

- Obtaining new scientific knowledge that shows that the study is no longer valid or necessary
- Insufficient recruitment of patients
- Persistent non-compliance with the protocol

If the study is discontinued or suspended prematurely, the Sponsor shall promptly inform all clinical investigator(s) / investigational center(s) of the termination or suspension and the reason(s) for this. The IRB/EC shall also be informed promptly and provided with the reason(s) for the termination or suspension by the Sponsor or by the Site PI / investigational center(s). Regulatory authorities and the personal physicians of the patients may also need to be informed if deemed necessary.

## 11.0 SITE CLOSE-OUT

At the time of the site close-out, the sponsor designee will collect all outstanding study documents, ensure that the Investigator's files are accurate and complete, review record retention requirements with the Investigator and ensure that all applicable requirements are met for the study. The observations and actions will be documented in a final closeout report.

## 12.0 RESPONSIBILITIES

Aerin Medical Inc. is the manufacturer of the Vivaer™ System and the Sponsor of this study. The study Sponsor has the overall responsibility of the study and will work to ensure compliance with

the Investigational Plan, elements of Good Clinical Practice: Consolidated Guidance (ICH, April 1996), signed study agreements and 21 CFR 812.2(b), *Abbreviated Requirements*.

The sponsor will be responsible for, but not limited to, conducting the following tasks:

- Select qualified Investigators
- Provide the Investigational Plan and any subsequent amendments
- Sign the protocol
- Provide appropriate information to Investigators and study site staff
- Promptly inform the Investigators and where applicable any regulatory authorities and Ethics Committees, if the study is prematurely terminated or suspended and the reason for the termination or suspension
- Provide protocol initiation training to include the Investigational Plan, CRF completion guidelines, and guidelines for obtaining informed consent
- Coordinate ongoing communication with consultants and study sites to resolve any problems concerning the protocol or data collection. Every effort will be made to ensure compliance with the protocol
- Retain ownership of all clinical data generated in this study, and control the use of the data for purposes of regulatory submissions to the US and other regulatory agencies
- Protect patient confidentiality
- Collect, store and keep secure, at a minimum, the following documents:
  - A current Curriculum Vitae and medical license of each Investigator
  - The name of the institutions where the study will be conducted
  - The IRB/EC opinion and / or approval, in writing, and relevant correspondence
  - Correspondence with authorities (as required)
  - Investigator Agreement
  - CIP Signature Page
  - Appropriate insurance certificates (as necessary)
  - IRB/EC Approved ICF
  - Names / contact information for study monitor(s)
  - Copies of signed and dated CRFs

### 13.0 SPONSOR MAINTENANCE OF STUDY RECORDS

The Sponsor will be responsible for **maintaining study records** per 21 CFR 812.140(b) and Good Clinical Practice: Consolidated Guidance (ICH, April 1996), Section 8.

The Sponsor will be responsible for **monitoring the investigation** per 21 CFR 812.46 and Good Clinical Practice: Consolidated Guidance (ICH, April 1996), Section 5.18.

The Sponsor will be responsible for **reporting** per 21 CFR 812.50(b).

